### **7.1.8 Inspections**

The investigator will make the source documents for this study available to Genentech, Inc. or its authorized designee, or to the regulatory or health authority inspectors.

## **8. Conflict of Interest**

The Sponsor-Investigator does not participate in any financial arrangement with the funding sponsor, Genentech other than for this study and its associated usual and customary fees; has no proprietary interest in this product or significant equity interest in Genentech; and was not and is not the recipient of significant payments of other sorts (as defined in 21 CFR 54.2(f))

APPENDIX A: SCHEDULE OF STUDY ASSESSMENTS & PROCEDURES

STUDY ASSESSMENTS & PROCEDURES	SCREENING PHASE	TREATMENT PHASE (1 YEAR)											POST TREATMENT FOLLOW UP (2 YEARS)							
	BASELINE VISIT	1 MONTH POST DOSING	2 MONTH POST DOSING	3 MONTH POST DOSING	4 MONTH POST DOSING	5 MONTH POST DOSING	6 MONTH POST DOSING	7 MONTH POST DOSING	8 MONTH POST DOSING	9 MONTH POST DOSING	10 MONTH POST DOSING	11 MONTH POST DOSING	1 YEAR POST DOSING	1 MONTH POST TREATMENT	2 MONTH POST TREATMENT	3 MONTH POST TREATMENT	7 MONTH POST TREATMENT	1 YEAR POST TREATMENT	2 YEARS POST TREATMENT	DISCONTINUATION VISIT
		+/- 7 DAYS																		
Informed Consent & Screening	X																			
Review of Inclusion/Exclusion Criteria	X																			
Review of Medical Records, if applicable	X	X	X	X	X	X	X	X	X	X	X	X	X	X	X	X	X	X	X	X
Medical/Dental History	X	X	X	X	X	X	X	X	X	X	X	X	X	X	X	X	X	X	X	X
Concomitant Medications	X	X	X	X	X	X	X	X	X	X	X	X	X	X	X	X	X	X	X	X
Demographics (height, weight)	X																			
Urine Pregnancy Test, if female patient of child bearing potential		X	X	X	X	X	X	X	X	X	X	X	X	X	X	X	X	X	X	X
Serum pregnancy test, if female patient of child bearing potential	X	*	*	*	*	*	*	*	*	*	*	*	*	*	*	*	*	*	*	*
Oral Cavity Assessment (soft & hard tissues)	X	X		X			X									X	X	X	X	
Physical Exam	X	X		X			X						X							X
Clinical Laboratories	X			X			X						X							X
Genetic Testing of Blood	X												X							X
Genetic Testing of the Tumor, if biopsy on excision	X												X							X
Vital Signs (BP, HR, temperature)	X	X		X			X						X				X	X	X	X
Verification of KCOT Diagnosis	X																			
Biopsy of Tumor, if applicable	X																			
Panoramic Radiograph	X	X		X			X						X				X	X	X	X
Volumetric CT Scan	X						X						X					X	X	X
Skin Examination for NBCCS-associated KCOT patients	X						X						X					X		X
Photographs of Skin Lesions, if applicable	X						X						X					X		X
Study Drug Administration – First Dose	X																			
Study Drug Dispense until next visit / Compliance with study drug	X	X	X	X	X	X	X	X	X	X	X	X	X							
Continuance Criteria/Study Reminders		X	X	X	X	X	X	X	X	X	X	X	X	X	X	X	X	X	X	
Adverse Events	X	X	X	X	X	X	X	X	X	X	X	X	X	X	X	X	X	X	X	X
Study completion, Discharge																				X

\* Any positive urine pregnancy test must be confirmed by a serum pregnancy test.

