**Table 9: Phase II BCNS Study (SHH4685s) Adverse Events Reported in ≥10% of Patients**

Number (%) of Patients with Grade 1 or 2 AEs	Vismodegib (n=26)	Placebo (n=15)	P Value
Taste disturbance, n	22 (85)	1 (7)	<0.001
Muscle cramps	21 (81)	0 (0)	<0.001
Hair loss	16 (62)	1 (7)	0.004
>5% weight decrease	11 (42)	0 (0)	0.003
GI upset	5 (19)	1 (7)	0.14
Acne	3 (12)	1 (7)	0.60

AE = adverse event; GI = gastrointestinal.

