## **2. STUDY OBJECTIVES**

### **2.1 Primary Objectives**

The primary objectives of the study are:

- a. To evaluate the efficacy of GDC-0449 in reducing KCOT size (shrinkage) in NBCCS-associated KCOT and sporadic KCOT patients following 6 to 12 months of ingestion of 150 mg/day, up to 1 year of treatment and up to 2 years of post-treatment follow-up.
- b. To evaluate the safety of this dose of GDC-0449 in these patients.

*Tumor response (reduction in tumor volume and shrinkage) will be measured by volumetric CT scan.*

*Time Frame: Efficacy will be assessed at 1 year and 2 years after the study medication is stopped. Patients will undergo evaluation for 3 years (up to 1 year of treatment and up to 2 years of post-treatment follow-up). All patients will participate in the assessment of the safety and tolerability of the study drug. Safety monitoring will capture risks related to study participation and adverse events related to the study drug.*

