### **Clinical Laboratories and Vital Signs**

Safety evaluations include clinical laboratory assessments as set forth in the Schedule of Study Assessments and Procedures in Appendix A. Safety and tolerability will be measured by adverse events, physical examination, complete blood count, vital signs, and oral cavity assessments. Details of laboratory procedures are provided in the laboratory manual for the study.

Samples of blood will be taken on selected visits (see Appendix A). 20 mL (inclusive) of blood will be obtained by venipuncture on each required visit. Approximately 100 mL of blood will be drawn over the course of the study (Screening through the completion of the Treatment Phase) for clinical laboratory assessments. Patients consenting to have a blood sample drawn for future DNA analysis will have an additional 7-10 mL of blood drawn at the baseline visit. Analysis of all clinical blood samples will be made at a central clinical laboratory. The investigator and clinical monitor will be provided with a list of the normal ranges used by the testing laboratory for all variables assayed during the study and a statement of accreditation (or similar) for the laboratory.

Complete blood count, serum pregnancy test, serum chemistry, coagulation time, and liver function will be assessed and include the following measures: white blood count, hemoglobin, platelets, glucose, uric acid, calcium, phosphorus, sodium, potassium, chloride, alkaline phosphatase, albumin, alanine transaminase (ALT), aspartate transaminase (AST), BUN and creatinine.

Female patients of childbearing potential will have a urine pregnancy test. A pregnancy test will be performed by the study center by use of a dipstick. All laboratory results will be reviewed and the reports signed by an investigator.

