Any results considered to be of clinical significance must be dealt with and followed up as clinically appropriate. All laboratory results considered to represent an adverse event (AE) must be documented in the case report form (CRF). Repeat samples will be taken if required for clinical follow up or because the sample is lost or damaged. Any abnormal end of treatment clinical laboratory result of clinical significance must be repeated at regular intervals until it returns to normal, or until an investigator is satisfied that the abnormality is not related to the drug and needs no further investigation. Vital signs (blood pressure, heart rate and temperature) will be obtained for safety monitoring.

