### **Oral Cavity Assessment, Head & Neck, & Physical Exam**

At the scheduled time points, according to the Schedule of Study Assessments and Procedures in Appendix A, study personnel will perform a comprehensive oral exam consisting of an evaluation of oral hard and soft tissue structures for each patient. Oral hard tissue assessments will be performed with a dental mirror on the teeth and bony structures. Oral soft tissues will be performed by examining each patient's mouth and pharynx, including lips, tongue, floor of the mouth, palate, gingiva, alveolar mucosa, buccal mucosa, oropharynx, tonsils, uvula, and salivary glands using palpation techniques and visualization.

A complete extraoral physical exam of the head and neck regions will also be noted by visualization and bi-manual palpation. This assessment will be performed during the baseline visit and the treatment and post-treatment phase of the study.

In addition to the oral hard tissue assessments, extraoral and head and neck examinations, a complete physical exam will be done during the baseline and treatment

phase of the study. This exam will include the examination of the cardiovascular, pulmonary, abdomen and nervous system.

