#### **4.4.2 Baseline Visit**

The following procedures will be performed at Baseline visit (study procedures and assessments during the baseline visit can be conducted over several visits until all inclusion/exclusion criteria are verified and patient is eligible to proceed with treatment (first study drug administration)).

After obtaining written Informed Consent for a potential subject, a unique Screening number will be assigned and the following evaluations will be performed to screen for eligibility:

- Informed Consent and Screening
- Review of Inclusion/Exclusion Criteria
- Review of Medical Records, if applicable
- Medical/Dental History
- Concomitant Medications
  - All prescription, non-prescription medicines, vitamins and herbal supplements will be recorded at the baseline visit in the concomitant medication CRF. Throughout the study, any changes in concomitant medication must be recorded by the investigator.
- Demographics (including height and weight)
  - In addition to the height and weight, the following information will be collected: date of birth, gender and race.

- Serum Pregnancy Test (if female patient of child bearing potential):
  - Female patients of reproductive potential are required to use two forms of acceptable contraception during therapy and for 24 months after completing therapy. See appendix B for definition of reproductive potential and acceptable contraception. Male patients must use condoms at all times, even after a vasectomy, during sexual intercourse with female partners of reproductive potential during treatment with vismodegib and for 2 months after the last dose to avoid exposing a pregnant partner and unborn fetus to vismodegib.
  - If 7 days have passed between the patient's enrollment in the study (date the ICF was signed) and the first study drug administration, the serum pregnancy test will be repeated.
  
- Oral Cavity Assessment (soft & hard tissues, extraoral, head & neck)
  
- Physical Exam
  
- Clinical Laboratories
  - Complete blood count, serum pregnancy test, serum chemistry, coagulation time, and liver function will be assessed: white blood count, hemoglobin, platelets, glucose, uric acid, calcium, phosphorus, sodium, potassium, chloride, alkaline phosphatase, albumin, alanine transaminase (ALT), aspartate transaminase (AST), BUN and creatinine

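### Body weight is scheduled at baseline only, so weight loss, a common effect of this drug, has no planned follow-up measurement

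*Combined protocol and SAP*

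**What the plan says.** Section 2.1 makes safety a primary objective: "To evaluate the safety of this dose of GDC-0449 in these patients". Section 4.4 (Clinical Laboratories and Vital Signs) names the measures: "Safety and tolerability will be measured by adverse events, physical examination, complete blood count, vital signs, and oral cavity assessments". Weight is not among them.

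Weight is collected once. The baseline list in Section 4.4.2 has "Demographics (including height and weight", and the matching row of Appendix A, "Demographics (height, weight", is marked at baseline only.

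The other assessments that might have included it do not:

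- Vital signs in the text: "Vital signs (blood pressure, heart rate and temperature) will be obtained for safety monitoring".
- Vital signs in Appendix A: "Vital Signs (BP, HR, temperature".
- Physical exam: "This exam will include the examination of the cardiovascular, pulmonary, abdomen and nervous system".
- The visit lists in Sections 4.4.3 and 4.4.4 contain no weighing.

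The potential-risks part of Section 4.4 puts weight loss among the most common reactions (incidence 10% or more). Table 9, from the Gorlin-syndrome trial, defines the event as ">5% weight decrease".

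**The concern.** Weight loss is a gradual, numeric effect, and its size is naturally expressed as a change from baseline. The plan collects the baseline value and schedules nothing to compare it with. What remains is adverse-event questioning, for which Section 5.3 gives general, non-directive examples that do not mention weight.

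At stake is how fully a known effect is described in a trial that has safety as a primary objective. There is no control arm, so readers will set the results beside the published rates. One of those, in the population closest to half of this trial's patients, is a percentage threshold that cannot be reproduced without later weights. A weight that was not taken cannot be recovered afterwards.

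**Working it through.** **Step 1: count the scheduled weights.** Appendix A has 12 treatment visits (months 1 to 11 and 1 year), 6 post-treatment visits (1, 2, 3 and 7 months, 1 and 2 years) and a discontinuation visit. The row containing weight is marked at none of them: 0 of 18 scheduled visits, and 0 at discontinuation.

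**Step 2: look for another route in the schedule.** On treatment, vital signs and the physical exam both fall at months 1, 3, 6 and 12, and both are also marked at discontinuation. Neither is described as including weight. The visits at months 2, 4, 5 and 7 to 11 have history, concomitant medication, urine pregnancy test, compliance and adverse events only.

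**Step 3: size of the effect in the protocol's own sources.** The plan states no expected weight-loss rate for this trial, so there is no figure of its own to reproduce. With p the cited rate and N = 20 (Section 4.8), the expected number of cases is 20p, and the chance of at least one is 1 − (1 − p)^20.

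| Source in Section 1.3 | Weight loss | p | 20p | P(at least 1) |
|---|---|---|---|---|
| Expanded access study, adverse-event table | 19/120 | 0.158 | 3.2 | 0.968 |
| Large phase II safety study (MO25616) | 32.4% of 500 | 0.324 | 6.5 | 0.9996 |
| Gorlin-syndrome trial, Table 9 (fall of more than 5%; 0/15 on placebo) | 11/26 | 0.423 | 8.5 | >0.999 |
| Pivotal phase II study, Table 6 | 53/104 | 0.510 | 10.2 | >0.999 |

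The range is about 3 to 10 of 20 patients. For grade 2 or higher, the pivotal study gives (17 + 7)/104 = 23.1%, or 20 × 24/104 = 4.6 patients. The expanded access study gives 7/120 = 5.8%, all grade 2, or 20 × 7/120 = 1.2 patients.

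**Step 4: timing.** The expanded access table gives a median onset of 175 days (95% CI 114 to 293) among affected patients. At 30.4 days per month that is 5.8 months (3.75 to 9.6). About half of the onsets in that study therefore came after roughly month 6. Weighing only at the vital-signs visits would leave nothing between months 6 and 12.

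**Step 5: what cannot be calculated.** Percent change is 100 × (W_t − W_0)/W_0. The plan supplies W_0 but no scheduled W_t. The share of true cases that adverse-event questioning would pick up is not given anywhere, so the number missed has no estimate.

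The detectable differences in Section 4.8 concern tumour volume and are unaffected.

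**The case against.** A reader might infer that the trial cannot detect or grade weight loss at all, or would learn of it only if a patient volunteers it. The documents do not support that. Adverse events are recorded at every visit. Section 5.2 accepts events found by questioning, examination or other means, and medical history is updated throughout. The potential-risks text promises close monitoring for known reactions. The Dermatologic Assessments text, which is generally worded, lets the investigator choose further safety assessments once an event is reported. With a baseline weight on file, one triggered weighing would give a percent change. The exam is also called complete, and its four systems are introduced as what it includes, which does not rule out a weight.

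A reader might also take only the two highest rates and expect 8 to 10 affected patients. The documents' own range starts at about 3.

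Other cautions stand. Apart from Table 9, the cited figures are adverse-event incidences, and the documents do not say they came from scheduled weighing. The CRFs are not in the file and pages after the Appendix D table were removed, so it cannot be judged whether a weight field or grading row exists. Safety is summarised descriptively, so no primary test or power figure changes.

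None of this supplies a scheduled weight. Triggered weighing depends on someone first noticing the loss, and an exam that could include weight does not require it.

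**Conclusion.** The point holds as a gap in measurement. If the plan is followed exactly, weight loss can enter the data as a reported or noticed adverse event. It cannot be detected systematically or quantified as percent change from baseline, and its incidence and severity are likely to be under-ascertained.

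The effect is frequent: about 3 to 10 of 20 patients at the cited rates. That range assumes the rates carry over to patients with keratocystic odontogenic tumours treated for up to a year. The sources differ in population, follow-up and definition, so it is context and not a forecast. The amount of under-ascertainment cannot be computed from the documents.

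This is a cheap improvement to the safety data. It does not affect the efficacy analysis.

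**What to change.** - **Appendix A and Section 4.4.3:** add body weight at all the existing on-treatment visits, including the monthly safety visits in months 7 to 11 and not only the visits with vital signs, and at the discontinuation visit.
- **Section 4.4.4 (optional):** add weight at the 7-month, 1-year and 2-year post-treatment visits, where vital signs are already taken.
- **Section 4.8.c:** summarise percent change from baseline weight by visit, and the proportion of patients with a loss of more than 5%, the definition in Table 9.
- **Grading:** Section 4.8.c names WHO toxicity criteria or protocol-specified criteria, while Appendix D presents NCI-CTCAE. These must be reconciled so that weight loss, like other events, is graded on one named scale.

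The cost is one scale reading and one CRF field per visit: at most 12 on-treatment readings per patient, or 20 × 12 = 240 in all, plus any discontinuation and optional post-treatment readings. No visits are added, and sample size and efficacy analyses stay as they are.

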## **APPENDIX B**

### **Definition of Women of Childbearing Potential and Acceptable and Unacceptable Forms of Contraception**

#### **Definition of childbearing potential**

Female patients who meet at least one of the following criteria are defined as women of **non-childbearing** potential:

- $\geq 50$  years old and naturally amenorrheic for  $\geq 1$  year
- Permanent premature ovarian failure confirmed by specialist gynecologist
- Previous bilateral salpingo-oophorectomy or hysterectomy
- XY karyotype, Turner's syndrome, or uterine agenesis

Female patients who do not meet at least one of the above criteria are defined as women of **childbearing** potential.

Additionally, the parent or guardian of young female patients who have not yet started menstruation should verify that menstruation has not begun. If a young female patient reaches menarche during the study, she is to be treated as a woman of childbearing potential from that time forward.

#### **Acceptable contraception**

Women of child-bearing potential must use two methods of acceptable contraception including one highly effective method and a barrier method during Erivedge therapy and for 9 months after the final dose.

Acceptable forms of barrier contraception include the following:

- Latex, non-latex, or any other male condom (always used with spermicide)
- Diaphragm (always used with spermicide)

Acceptable forms of secondary contraception, when used with a barrier method, include the following:

- Combination hormonal contraceptives, hormonal patch, or hormonal intramuscular contraceptives (subcutaneous hormonal implant, medroxyprogesterone acetate depot)
- Tubal sterilization

Other acceptable forms include the following:

- 100% commitment to abstinence from sexual intercourse (for medical or personal reasons)

**Unacceptable contraception**

The following are unacceptable forms of contraception:

- IUD progesterone T
- Progestin-only contraceptives
- Female condom
- Natural family planning (rhythm method) or breastfeeding
- Fertility awareness
- Withdrawal
- Cervical shield
- Vaginal contraceptive ring

**NOTE:** Patients should be counseled on the use of contraception before beginning treatment with vismodegib. As appropriate, the treating physician should refer the subject to her gynecologist or other healthcare provider to ensure proper understanding of the use of her chosen contraceptive method.

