## **4. MATERIALS AND METHODS**

### **4.1 Subject Selection**

#### **4.1.1 Inclusion Criteria**

Patients are eligible to participate in the study if they meet the following criteria:

- Males and females, 18 years of age and above at the time the informed consent form is signed;
- Able to understand and sign the Informed Consent Form and other necessary paperwork prior to initiation of study procedures;
- Able to communicate with the investigator/study site personnel, understand and comply with the study requirements, and willing to return for specified visits at the appointed time;
- Patients who have received prior treatment for their KCOT and with a diagnosis of recurrent (maxillary or mandibular) sporadic KCOT or NBCCS-associated KCOT (single or multiple);
- Diagnosis of KCOT will be done by past pathology report or by biopsy at the study site, if applicable;
- Willingness to consent to biopsy of the lesion, if needed;
- Willingness to delay excision of the target tumor site, unless evidence of disease progression or lack of drug tolerability;
- For female patients of childbearing potential, agreement to use two acceptable methods of birth control, including one barrier method during the study and 24 months after discontinuation of study drug;
- For males with female partners of childbearing potential, agreement to use a male condom (with spermicide) and to advise their female partners to use an acceptable method of birth control during the study and for 3 months after the discontinuation of the study drug;
- Agreement not to donate blood/blood products during the study and for 24 months after the discontinuation of the study drug;
- For males not to donate sperm products or semen during treatment and for 3 months after the discontinuation of the study drug;
- Able and willing to swallow pill;

- No malabsorption syndrome or other condition that would interfere with enteral absorption;
- At least 4 weeks since last chemotherapy, investigational therapy, radiotherapy or major surgical procedure and recovered from the first study drug administration;
- KCOT measures at least 1 cm in one dimension on pretreatment volumetric CT scan;
- No clinically significant abnormalities with clinical laboratory assessments;

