The safety and efficacy of vismodegib in pediatric patients has not been established. Studies in animals indicate that oral Hh pathway inhibitors pose a substantial risk of developmental defects during the post-natal period, which includes irreversible effects on growing teeth or bones and male reproductive organs. The occurrence of premature epiphyseal fusion has been identified on routine pharmacovigilance through literature review and from serious adverse events (SAEs) reported in an Investigator Sponsored Trial (IST) of pediatric patients receiving vismodegib therapy. In some cases, fusion progressed after drug discontinuation.

In this study, the safety and efficacy of oral GDC-0449 in the management of NBCCS-associated KCOT and sporadic KCOT will be examined. The recommended dose is 150mg taken orally once daily until disease progression or until unacceptable toxicity. The capsule has a pink opaque body and a grey opaque cap with "150 mg" printed on the capsule body and "Vismo" printed on the capsule cap in black ink. It can be taken

with or without food and capsules should not be opened or crushed. If patients miss a dose, they will be advised not to make up that dose but instead to resume dosing with the next scheduled dose.

Pregnancy status prior to the initiation of GDC-0449 will be verified with a serum pregnancy test. Male and female patients will be advised of the risks of embryo-fetal death and severe birth defects and the need for contraception during and after treatment.

In addition, patients must agree not to donate blood or blood products during the study and for 24 months after discontinuation of vismodegib.

If a patient experiences unacceptable drug toxicity, he/she will be allowed a treatment break lasting for at least one month, up to three months. If the patient is unable to resume treatment after an 3 month treatment break, he/she will be discontinued from the study.

A potential risk of treatment of KCOT with vismodegib is disease progression, *i.e.* tumor growth. Participants will be closely monitored with clinical and radiographic examination for evidence of disease progression. The natural history of KCOTs is that the tumors grow and expand slowly relative to the proposed examination schedule. Therefore, it is highly unlikely that unanticipated growth in participants on vismodegib would be encountered.

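### Appendix B names depot medroxyprogesterone acetate as acceptable contraception, then rules out progestin-only contraceptives without exception

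*Combined protocol and SAP*

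**What the plan says.** Appendix B has two consecutive lists.

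- **Acceptable contraception.** After the barrier methods comes a second group, introduced by "Acceptable forms of secondary contraception, when used with a barrier method, include the following". It covers combination hormonal products, the patch, and "hormonal intramuscular contraceptives (subcutaneous hormonal implant, medroxyprogesterone acetate depot". Tubal sterilization follows as a separate item.
- **Unacceptable contraception.** This list opens with "The following are unacceptable forms of contraception". One of its entries is "Progestin-only contraceptives".

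Other parts of the protocol depend on these lists. Section 4.1.1 (Inclusion Criteria) requires from women of childbearing potential "agreement to use two acceptable methods of birth control, including one barrier method during the study", and for a period afterwards. Section 4.4.2 (Baseline Visit) tells staff: "See appendix B for definition of reproductive potential and acceptable contraception". The treatment and post-treatment visit instructions in sections 4.4.3 and 4.4.4 refer back to Appendix B when patients are reminded not to become pregnant. Under Potential Risks to Participants, section 4.4, patients are to be "advised of the risks of embryo-fetal death and severe birth defects and the need for contraception during and after treatment".

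**The concern.** A coordinator who has to decide whether a woman's method counts as acceptable will look in Appendix B. For the depot injection, the answer depends on which list is read. The first names the product and permits it with a barrier method. The second excludes the class to which it belongs.

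What is at stake is consistent application of a pregnancy precaution. Two members of staff could counsel two women differently about the same method, or accept it from one and refuse it from the other, and each could point to the text in support. Patient materials drawn from the appendix would carry the same conflict.

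**Working it through.** No arithmetic applies. The check sets the two lists side by side and asks whether anything in the protocol resolves them.

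1. **Status of the text.** Both lists are current text in Appendix B. Neither is part of a change log, and nothing is blacked out there.

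2. **Depot medroxyprogesterone acetate.** The acceptable list names it. To place it on the other list, one needs to know that it is a progestin given without an estrogen. The documents do not state its composition. However, that is the plain meaning of the generic drug name, and staff cannot apply the progestin-only entry at all without knowledge of this kind. On that footing the product is permitted by name in one list and excluded by class in the next.

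3. **Subcutaneous hormonal implant.** The acceptable list names it, but only as hormonal, and no hormone is given. It falls in the excluded class only if it contains a progestin alone. That is an assumption, so the conflict over the implant is conditional.

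4. **Does the barrier condition reconcile the lists?** No. The acceptable list attaches a barrier method to every secondary method. The unacceptable list has no matching condition, such as an exclusion that applies only when no barrier is used.

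5. **Does a limit by route reconcile them?** No. The excluded entry is not restricted to oral products or to any other form.

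6. **Is there a rule of precedence?** None was found in Appendix B, in section 4.1.1 or in section 4.4.2.

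7. **Does the closing note in Appendix B settle it?** No. It provides for counselling and, where appropriate, referral to a gynecologist so that the woman understands the method she has chosen. It does not say whether that method is allowed.

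8. **Who could be affected?** Section 3.1 plans 20 enrolled patients, 10 in each cohort. The affected group is the women of childbearing potential among them who use or choose one of these two methods. The documents give neither the share of women nor the mix of methods, so the number can only be bounded: from 0 to at most 20.

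**The case against.** The strongest reply is that a workable reading exists. The acceptable list is specific, and a reader may let a named product override a general class. The authors may also have meant progestin-only pills. The unacceptable list gives a progesterone intrauterine device its own line, which could suggest that the progestin-only entry was meant narrowly. These readings are plausible, but the text states none of them, and a reader who takes the unacceptable list at its word is not misreading it. To adopt one of these readings is to make the clarification that is missing.

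A second reply concerns the consequences, and much of it stands. The protocol has several layers of protection:

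- A barrier method is required in any case.
- Section 4.4.2 requires a serum pregnancy test at baseline, repeated if 7 days pass between consent and the first dose.
- Appendix A schedules a urine test at every later visit, and a positive result must be confirmed by a serum test.
- Section 4.6 withdraws a woman once pregnancy is confirmed.

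Three stronger readings are tempting, and the documents do not support them:

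- **That a depot user is both eligible and ineligible.** Section 4.1.1 asks for agreement to use two acceptable methods. It does not test the method in use at screening. A woman who agrees to another listed method qualifies whichever list is followed.
- **That the method list is the main safeguard against exposure in pregnancy.** The protocol does not rank its precautions, and the layers above would remain.
- **That the protocol states that the drug causes birth defects.** Its wording is about risks, and this point needs no more than that.

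**Conclusion.** Wrong as written, in a narrow sense. Appendix B contradicts itself on depot medroxyprogesterone acetate. This rests only on the product being a progestin without estrogen, as its generic name indicates. For the subcutaneous hormonal implant the contradiction is conditional on progestin-only content, which the documents do not give.

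The practical result is possible inconsistency in counselling and in accepting a method. The documents do not show that any woman would be wrongly enrolled or left unprotected. The number affected cannot be derived and may be zero. No endpoint, analysis or sample size is touched. The point still deserves correction because the instruction concerns a serious stated risk, and the remaining precautions reduce the consequence without telling staff which list to follow.

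**What to change.** The sponsor-investigator should reconcile the two lists in Appendix B so that each method falls on only one of them, and should state explicitly how the depot injection and the subcutaneous implant are classed. If the progestin-only entry was meant to cover certain forms only, the entry should name those forms. Patient materials that describe acceptable contraception should then be brought into line. This review takes no position on which methods should be allowed.

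The cost is a few words in the appendix and matching edits to patient materials, submitted to the IRB as section 7.1.2 requires for amendments and study materials. No visit, test or analysis changes.
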